11.6.2. Study Population

Demographics
Age

 GSK standard IDSL algorithms will be used for calculating age where birth date will be imputed as follows: 
 Missing date and month will be imputed as '30th June'. Birth date will be presented in listings as 'YYYY'.
Body Mass Index (BMI)

 Calculated as Weight (kg) / [Height (m)]²
Standardized rhEPO

For this study, ESA dose can be administered in five different ways: epoetin IV (Intravenous), epoetin SC (Subcutaneous), darbepoetin IV, darbepoetin SC or Mircera IV. The dose of ESA will be standardized to obtain a continuous single unit of prior ESA dose in terms of epoetin IV IU/kg/week. The standardization will be carried out using the formula:
 
 Weekly darbepoetin IV or SC dose (mcg) = Weekly epoetin IV dose (IU)/200 113 epoetin IV = 161 epoetin SC [Besarab et al] 
 For subjects taking epoetin IV no adjustment is needed. 
 $\text{Standardized rhEPO IV dose (IU/kg/week)} = \frac{\text{epoetin IV dose (IU)}}{(\text{frequency} * \text{weight (kg)})}$ 
 For subjects taking darbepoetin (IV or SC), their dose will be converted as follows: 
 $\text{Standardized rhEPO IV dose (IU/kg/week)} = \frac{(\text{darbepoetin dose (mcg)} * 200)}{(\text{frequency} * \text{weight (kg)})}$ 
 For subjects taking epoetin SC, their dose will be converted as follows: 
 $\text{Standardized rhEPO IV dose (IU/kg/week)} = \frac{161/113 * (\text{epoetin SC dose (units)})}{(\text{frequency} * \text{weight (kg)})}$ 
 For subjects taking Mircera (IV), their dose will be converted as follows: 
 $\text{Standardized rhEPO IV dose (IU/kg/week)} = \frac{(\text{Mircera dose (mcg)})}{(1.2 * \text{frequency} * \text{weight (kg)})}$ 
 
Where frequency = 4 if the subject takes the Mircera dose once every 4 weeks (Note: Once a month (QM) will be handled same as once every 4 weeks.), 2 if the subject takes the darbepoetin or Mircera dose once every 2 weeks, 1 if the subject takes the darbepoetin dose once a week, 0.5 if the subject takes the epoetin dose 2 times a week, 0.333 if the

Demographics

subject takes the epoetin dose 3 times a week etc. (For dose frequency = ONCE, please see the algorithm described later in this section.) Note, weight is the weight recorded at screening Week -2. If the screening weight is missing, the baseline weight will be used.

If a subject has multiple doses of prior ESA during the 12 weeks prior to randomization, the weighted mean would be calculated to obtain the standardized rhEPO.

In order to account for changes in ESA dose and pauses in ESA dose, the following algorithm will be used to determine the average weekly dose per subject over the 12-week period prior to randomization:

1. Derive the standardized weekly dose in terms of Epoetin IV (IU/kg/week) for each dose recorded in the eCRF during the 12-week period of interest, as detailed above. (Note, where the first dose started after the cutoff date for the 12-week period, defined by “randomization date – 12 weeks”, the dose prior to the first dose start date will be assumed to be 0. When the first dose started before the cutoff date defined by “randomization date – 12 weeks”, first day of the period (i.e. Randomization date – 12 weeks) is defaulted as the start date of that dose.)
2. Convert dose into units of dose per day (IU/kg/day) by dividing the weekly dose from step 1 by 7.
Standardized rhEPO IV Daily Dose (IU/kg/day) = Standardized rhEPO IV weekly dose IU/kg/week) / 7
3. Identify whether a pause in dosing has occurred, i.e. a period of time deemed to be a break from the planned treatment regimen, for each dose recorded. A pause in dosing will be identified as follows. In the table below, Dose 1 refers to the dose received before the pause (if one exists), and Dose 2 to the dose received after the pause (if one exists).

Dosing Regimen	Definition of a pause in dosing	Criteria for dosing pause	Gap factor (days) (to be added to stop date if dose pause exists)
3 times per week	3 or more days where no dose is administered	(Start Date Dose 2) – (Stop Date Dose 1) > 3	2
2 times per week	5 or more days where no dose is administered	(Start Date Dose 2) – (Stop Date Dose 1) > 5	4
1 times per week	8 or more days where no dose is	(Start Date Dose 2) – (Stop Date Dose 1) > 8	7

Demographics				
		administered		
0.5 times per week	15 or more days where no dose is administered	(Start Date Dose 2) – (Stop Date Dose 1) > 15		14
0.33 times per week	22 or more days where no dose is administered	(Start Date Dose 2) – (Stop Date Dose 1) > 22		21
0.25 times per week	29 or more days where no dose is administered	(Start Date Dose 2) – (Stop Date Dose 1) > 29		28

4. Calculate the duration of dose for each dose received. (Note that the duration of a dose will be capped at the start date of a new dose (Start Date Dose 2) or at randomization date.)

If a pause was identified between doses, the duration of dosing will be defined as follows:

$$\begin{aligned} \text{(Duration of Dose 1)} &= (\text{Stop Date Dose 1}) + (\text{Gap Factor}) - (\text{Start Date Dose 1}) + 1 \\ &= \text{Min}(\text{Randomization Date, Start Date Dose 2, Stop Date Dose 1} + \text{Gap Factor} + 1) - \text{Start Date Dose 1} \end{aligned}$$

If no pause was identified between doses, the duration of dosing will be defined as follows:

$$\begin{aligned} \text{(Duration of Dose 1)} &= (\text{Stop Date Dose 1} + \text{Gap factor}) - (\text{Start Date Dose 1}) + 1 \\ &= \text{Min}(\text{Randomization Date, Start Date Dose 2, Stop Date Dose 1} + \text{Gap Factor} + 1) - (\text{Start Date Dose 1}) \end{aligned}$$

5. Calculate the actual dose received for each dose, by multiplying the daily dose from step 2 by the duration of dose derived in step 4:

$$\text{Actual Dose (IU/kg)} = \text{Daily Dose (IU/kg/day)} \times \text{Duration of Dose (days)}$$

6. Calculate the total cumulative dose received over the subject’s 12-week period prior to randomization:

$$\text{Cumulative Dose (IU/kg)} = \text{Sum of all Actual Doses from step 5 (IU/kg)}$$

7. Calculate the average weekly dose over the 12-week period prior to randomization, by dividing the cumulative dose from step 6 by the duration of the 12-week period

Demographics

Average Dose (IU/kg/week) = Cumulative Dose (IU/kg)/12

For the special situation of dose frequency = “ONCE”, the following algorithm will be followed: (Note: Only for dosing within the 12-week period prior to randomization (i.e. randomization date – 12 weeks)).

1. Calculate the standardized rhEPO IV dose (IU/kg) for this specific prior ESA use
 - 1) For subjects taking epoetin IV no adjustment is needed.

$$\text{Standardized rhEPO IV dose (IU/kg)} = \text{epoetin IV dose (IU)} / (\text{weight (kg)})$$

- 2) For subjects taking darbepoetin (IV or SC), their dose will be converted as follows:

$$\text{Standardized rhEPO IV dose (IU/kg)} = (\text{darbepoetin dose (mcg)} * 200) / (\text{weight (kg)})$$

- 3) For subjects taking epoetin SC, their dose will be converted as follows:

$$\text{Standardized rhEPO IV dose (IU/kg)} = 161/113 * (\text{epoetin SC dose (units)}) / (\text{weight (kg)})$$

- 4) For subjects taking Mircera (IV), their dose will be converted as follows:

$$\text{Standardized rhEPO IV dose (IU/kg)} = (\text{Mircera dose (mcg)}) / (1.2 * \text{weight (kg)})$$

2. If all the records of prior ESA use during the 12-week period prior to randomization have dose frequency = “ONCE”, then:

$$\text{Standardized rhEPO IV dose (IU/kg/week)} = \text{Sum of Standardized rhEPO IV dose (s) (IU/kg)} / 12$$

Note: This includes the situations when either a subject has only one prior ESA use record with dose frequency = “ONCE” or a subject has more than one prior ESA use records and all of them have dose frequency = “ONCE”.

3. If, in addition to the prior ESA use record(s) with dose frequency = “ONCE”, a subject has other ESA use record(s) with different dose frequency during the 12-week period prior to randomization, then the Standardized rhEPO IV doses calculated from Step 1 in terms of epoetin IV (IU/kg) will contribute directly (without considering “Gap Factor”) to the total Cumulative Dose derived in Step 6 of calculation of average weekly dose.

Extent of Exposure

- Number of days of exposure to study drug will be calculated based on the formula:
Duration of Exposure in Days = Treatment Stop Date – Treatment Start Date + 1
- Subjects who were randomized but did not report a treatment start date will be categorised as having zero days of exposure.
- The cumulative dose will be based on the formula:
Cumulative Dose = Sum (Each dose taken recorded in the eCRF, including the dose taken on or prior to PK day Day 15 study visit)

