5.2. Inclusion Criteria

A subject will be eligible for inclusion in this study only if all of the following criteria apply:

AGE

1. \geq 18 years of age, at the time of signing the informed consent.

TYPE OF SUBJECT AND DIAGNOSIS INCLUDING DISEASE SEVERITY

- 2. **Hemoglobin**: Stable Hgb 9.0 11.5 g/dL (see Section 5.1).
- 3. **Dialysis frequency**: On hemodialysis (HD, hemofiltration or hemodiafiltration) three to five times weekly for at least 4 weeks prior to Day -28 Screening through Day 29.
- 4. **Dialysis adequacy**: A single pool Kt/V_{urea} of ≥1.2 based on a historical value obtained within the prior three months in order to ensure the adequacy of dialysis. If Kt/V_{urea} is not available, then an average of the last 2 values of urea reduction ratio (URR) of at least 65%. **NOTE**: Only needs confirming at Day -28.
- 5. **Stable ESA dose**: Treated with the same ESA (epoetins or their biosimilars, or darbepoetin or methoxy PEG-epoetin beta) with total weekly dose varying by no more than 50% from 4 weeks prior to Day -28 through Day 1 (randomization).
- 6. **Iron replacement therapy**: Subjects may be on maintenance oral or IV iron

supplementation. If subjects are on oral iron, then the type of iron and doses must not be changed for the 4 weeks prior to Day -28, during the screening phase, and through the 29 days of treatment. If subjects are on IV iron, then doses must be ≤100 mg/week, and doses must not be changed for the 4 weeks prior to Day -28, during the screening phase, and through the 29 days of treatment.

INFORMED CONSENT

7. Capable of giving signed informed consent as described in Section 10.2, which includes compliance with the requirements and restrictions listed in the consent form and in this protocol.

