5.3. Exclusion Criteria

A subject will not be eligible for inclusion in this study if any of the following criteria apply:

CKD-RELATED CRITERIA

- 1. **Dialysis modality**: Planned change from HD to peritoneal dialysis within the study time period.
- 2. **Renal transplant**: Planned for living-related or living-unrelated kidney transplant.
- 3. **High ESA dose**: An epoetin dose of ≥360 IU/kg/week IV or ≥250 IU/kg/week subcutaneous (SC) or darbepoetin dose of ≥1.8 µg/kg/week IV or SC or methoxy PEG-epoetin beta dose of ≥2.2 µg/kg/week within the prior 8 weeks through Day 1 (randomization).
- 4. **Mircera**: Administration of Mircera (methoxy PEG-epoetin beta) within 2 weeks prior to Day 1 if subject is on a once-every-2-weeks schedule or within 4 weeks prior to Day 1 if subject is on a once-every-4-weeks schedule.

CARDIOVASCULAR DISEASE-RELATED CRITERIA

- 5. **Myocardial infarction or acute coronary syndrome:** Within the 8 weeks prior to Screening through Day 1 (randomization).
- 6. **Stroke or transient ischemic attack:** Within 8 weeks prior to Screening through Day 1 (randomization).
- 7. **Heart failure:** Class IV heart failure, as defined by the New York Heart Association (NYHA) functional classification system diagnosed prior to Screening through Day 1 (randomization).
- 8. **QTcB:** QTcB >500 msec or QTcB >530 msec in subjects with Bundle Branch Block. There is no QTc exclusion for subjects with a predominantly paced rhythm.

OTHER DISEASE-RELATED CRITERIA

- 9. **Inflammatory disease:** Active chronic inflammatory disease that could impact erythropoiesis (e.g., scleroderma, systemic lupus erythematosis, rheumatoid arthritis, celiac disease) diagnosed prior to Screening through Day 1 (randomization).
- 10. **Hematological disease**: Any hematological disease including those affecting platelets, white or red blood cells (e.g., sickle cell anemia, myelodysplastic syndromes, hematological malignancy, myeloma, hemolytic anemia and thalassemia), coagulation disorders (e.g., antiphospholipid syndrome, Protein C or S deficiency), or

- any other cause of anemia of chronic disease other than renal disease diagnosed prior to Screening through Day 1 (randomization).

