6.2.4. Demography

Demographic and baseline data will include age, gender, ethnicity, race, diabetes, baseline height, baseline weight, baseline body mass index (BMI), prior ESA dose (stratification factor, Low ESA dose: <100 IU/kg/week epoetin OR <0.5 µg/kg/week darbepoetin OR <0.6 µg/kg/week methoxy PEG-epoetin beta vs. High ESA dose: ≥100 IU/kg/week epoetin OR ≥0.5 µg/kg/week darbepoetin OR ≥0.6 µg/kg/week methoxy PEG-epoetin beta), type of ESA, standardized prior rhEPO Dose (IU/kg/Week, including epoetin, darbepoetin, and Mircera), baseline Hgb, baseline ferritin, baseline absolute reticulocyte count, baseline iron-based phosphate binder (ferric citrate and sucroferric oxyhydroxide), and baseline pre-dose plasma EPO. In addition, the following data will be categorized and summarized for each treatment group and overall:

- Age (<65, ≥65 years)
- Baseline Hgb (< 10, ≥ 10 g/dL)
- Baseline Weight (≤Median, > Median kg)
- Baseline BMI (<27, ≥27 kg/m²)
- Race (White, African American, Asian, Other)
- Standardized Prior rhEPO (≤xx.xx, >xx.xx and < xx.xx, ≥xx.xx) (Tertile)
- Diabetes (Yes, No)
- Iron-based Phosphate Binders (Yes, No)
- Baseline Absolute Reticulocyte Count (≤ Median, >Median TI/L)

All the above demographic and baseline data will be summarized by treatment group and overall for the Safety, ITT and All Randomized populations.

A by-subject listing of demographic and baseline characteristics will also be produced.

Summaries of race and racial combinations and race and racial combination details will be produced for each treatment group and overall. A listing of race and racial combination details by subject will also be produced.

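### Both Mircera conversions in the SAP omit the ×200 step, so a Mircera user's standardized prior rhEPO dose comes out 200 times too small

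*SAP*

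**What the plan says.** SAP 11.6.2 (Standardized rhEPO) converts each prior ESA to epoetin IV in IU/kg/week and averages over the 12 weeks before randomization. It states the darbepoetin rule outright: "Weekly darbepoetin IV or SC dose (mcg) = Weekly epoetin IV dose (IU)/200". The darbepoetin formula applies it, with "darbepoetin dose (mcg)} * 200" in the numerator. The Mircera formula has "Mircera dose (mcg)})}{(1.2" × frequency × weight), with no 200, and its result is labelled IU/kg/week. The separate formulas for a dose recorded as ONCE repeat the pattern: darbepoetin carries the 200, and Mircera is "Mircera dose (mcg)}) / (1.2" × weight), labelled IU/kg. No Mircera equivalence is listed beside those for darbepoetin and SC epoetin.

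The plan gives parallel cut-offs for the three agents elsewhere. SAP 6.2.4 defines the low stratum as "Low ESA dose: <100 IU/kg/week epoetin OR <0.5" µg/kg/week for darbepoetin and, continuing, "kg/week darbepoetin OR <0.6" µg/kg/week for Mircera. Protocol 5.3, criterion 3, excludes epoetin IV from 360 IU/kg/week, darbepoetin from 1.8 µg/kg/week, and a "methoxy PEG-epoetin beta dose of ≥2.2" µg/kg/week.

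**The concern.** Dividing Mircera micrograms by 1.2 yields another microgram figure, on the darbepoetin scale. Calling it IU mixes two units in one variable.

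That variable is used in the baseline tables (1.10 to 1.12), the prior-dose histogram (Figure 1.2), Listing 9 and the tertile subgroup of SAP 11.10.1, which Tables 2.3 and 2.4 call for. If the formulas are programmed as written, a Mircera user's position in the dose distribution reflects the product and not the dose, so any difference across dose tertiles is mixed with a difference between agents. Tertiles pass the rule of at least 30% of ITT subjects per subgroup by construction. The three-level Type of Prior ESA subgroup, which would help to separate the two, passes only if every agent holds 30% to 40% of subjects, unless categories are refined before unblinding.

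**Working it through.** **Inputs**
- Target unit epoetin IV, IU/kg/week; 1 mcg darbepoetin = 200 IU epoetin IV; average over 12 weeks (SAP 11.6.2).
- Stratum cut-offs per kg per week: 100 IU epoetin, 0.5 mcg darbepoetin, 0.6 mcg Mircera (Protocol 4.1; SAP 6.2.4 and 11.10.1).
- Exclusion limits per kg per week: 360 IU epoetin IV, 1.8 mcg darbepoetin, 2.2 mcg Mircera (Protocol 5.3).
- Same-ESA requirement "from 4 weeks prior to Day -28 through Day 1 (randomization") in Protocol 5.2, criterion 5: about the last 8 of the 12 averaged weeks.

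**1. Darbepoetin formula against the plan's own cut-offs.** 0.5 × 200 = 100 and 1.8 × 200 = 360. Both agree exactly.

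**2. Mircera formula as written.** 0.6/1.2 = 0.5, against 100. 2.2/1.2 = 1.83, against 360. Neither agrees. The value 0.5 is the darbepoetin cut-off in micrograms, which shows what the 1.2 does.

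**3. Mircera formula with ×200.** 0.6 × 200/1.2 = 100, exact. 2.2 × 200/1.2 = 366.7 against 360, which is 1.9% off and consistent with a rounded limit (1.8 × 1.2 = 2.16).

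**4. ONCE formula.** Take three single doses of 2.4 mcg/kg in 12 weeks, equal to 0.6 mcg/kg/week. As written: 3 × 2.4/1.2/12 = 0.5. With ×200: 100.

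**5. Other possible slips, at 0.6 mcg/kg/week.** Multiplying by 1.2 gives 0.72. Dropping the 1.2 gives 0.6. Applying the SC factor 161/113 to 0.5 gives 0.71. None approaches 100.

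**6. Subjects who changed agent.** Epoetin IV 100 IU/kg/week for 4 weeks, then Mircera 0.6 mcg/kg/week for 8: (4 × 100 + 8 × 0.5)/12 = 33.7 instead of 100, a factor of 100/33.7 = 3.0.

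**7. Tertiles.** The documents do not give the Mircera share m. Assume that all Mircera users are on it for the full window and have the same true dose distribution as other subjects. For m up to one third, all of them fall in the lowest tertile, where only m/3 of all subjects (one third of the Mircera users) belong. So 2m/3 of all subjects are wrongly there, which is 2m of that tertile. They push 2m/3 of all subjects (non-Mircera) from low to middle, and m/3 then move from middle to high. Total misclassified: 2m/3 + 2m/3 + m/3 = 5m/3.

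| m | Share of lowest tertile wrongly placed Mircera users (2m) | All subjects in wrong tertile (5m/3) | Of 90 |
|---|---|---|---|
| 0% | 0% | 0% | 0 |
| 2% | 4% | 3% | 3 |
| 5% | 10% | 8% | 7.5 |
| 10% | 20% | 17% | 15 |
| 20% | 40% | 33% | 30 |
| 30% | 60% | 50% | 45 |

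Above one third, the lowest tertile contains only Mircera users. It takes in (1/3)/0.40 = 83% of them at m = 40% and (1/3)/0.50 = 67% at m = 50%.

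**The case against.** The omission itself is hard to dispute: it occurs in two separately written formulas, and the 1.2 is present in both. The case on the other side concerns certainty and weight.

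- **The equivalence is inferred.** This stands. The SAP never states it, and the exclusion limits agree only approximately (367 against 360). The stratum cut-offs agree exactly, but the sponsor should confirm the value.
- **The Mircera share is unknown.** This stands too. With no Mircera users nothing changes, and at 2% only about 3 of 90 subjects move. Equal dose distributions across agents is also an assumption.
- **The error would be visible.** Partly so. Listing 9 shows ESA type beside standardized dose, and values below 2 IU/kg/week should stand out in the histogram. No planned step is designed to catch it, however, and the missing equivalence line gives a programmer nothing to check against.
- **Little depends on the variable.** Largely true. No hypothesis is tested, and the Low/High prior-ESA subgroup uses agent-specific cut-offs and needs no conversion. With 90 subjects, five arms and three tertiles leave 90/15 = 6 per cell. This limits the severity but does not make the formula right.
- **One loose end.** Listing 9 also has a Standardized Prior ESA Category taken from eCRF values, whose derivation is not given. If it compares the standardized dose with 100, it is affected as well.

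**Conclusion.** The concern holds: both Mircera formulas are wrong as written. The error is 200-fold for a subject on Mircera throughout the 12 weeks (0.5 instead of 100 IU/kg/week at the stratum cut-off) and smaller for one who changed agent (3-fold in the example). At a steady eligible dose, a full-window Mircera user scores below about 1.83 IU/kg/week. The factor of 200 rests on the plan's darbepoetin rule, its 1.2 divisor and its parallel cut-offs. The misclassification figures rest on an assumed Mircera share and equal true dose distributions, and are illustrations.

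The damage is confined to the baseline description and one subgroup. Randomization, the Low/High stratification factor, the primary Emax model and the dose-ratio analyses do not use the variable. It should be corrected before unblinding, but it does not threaten the primary result.

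**What to change.** In SAP 11.6.2:
- Add a Mircera line to the list of equivalences. The cut-offs imply 1.2 mcg Mircera = 1 mcg darbepoetin = 200 IU epoetin IV; the sponsor should confirm this.
- Change the regular formula to (Mircera mcg × 200)/(1.2 × frequency × weight).
- Change the ONCE formula to (Mircera mcg × 200)/(1.2 × weight).
- Add a programming check that 0.6 mcg/kg/week returns 100 IU/kg/week by both routes.
- State how the Standardized Prior ESA Category in Listing 9 is derived.

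The cost is one equivalence line, one factor in two formulas, a sentence on Listing 9 and the matching program lines. If this is done before unblinding, the change cannot be suspected of being driven by the results. It corrects a data derivation and alters no treatment rule.

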11.2. Appendix 2: Time & Events

11.2.1. Protocol Defined Time & Events

Protocol Activity ^{1,2}	Screening		Day 1	Treatment Period				Follow-up
	Week -4	Week -2		Day 15	Day 29	Un-scheduled	Early Withdrawal	Day 43 ± 3 ⁶
Informed Consent	X							
Entry Criteria	X		X					
Physical, Medical History, Demography	X							
HemoCue Hgb	X	X	X	X	X	X	X	
IVWRS Call	X	X	X	X	X	X	X	X
Females Only: Serum Pregnancy Test ³		X					X	X
Females Only: Estradiol and FSH (if required) ³		X						
ECG	X				X		X	
Vitals (Pre-dialysis and Post-dialysis) ⁴		X	X	X	X	X	X	X
Clinical Chemistry		X	X	X	X	X	X	X
Hematology		X	X	X	X	X	X	X
Folate and Vitamin B ₁₂	X							
Ferritin, transferrin, total iron, UIBC	X		X		X		X	X
Pharmacokinetic/Pharmacodynamic Samples			X	X	X		X ⁵	
Blood draw for PGx			X					
Adverse Events Assessment ⁷			X	X	X	X	X	X
Review Concomitant Medications	X		X	X	X	X	X	X

¹ All assessments should be done pre-dialysis except as noted.

² Allowable time window of ± 2 days for all study visits, except the follow-up visit for which it is ± 3 days.

³ As detailed in Inclusion Criteria in study protocol Section 5.2

⁴ Weight measured post-dialysis only & height measured at screening only.

⁵ Obtain samples as per the Day 29 visit in Table 2 of the study protocol. If subject does not receive a dose of study medication at this early withdrawal visit, no post-dose PK/PD samples should be obtained.

⁶ Subjects who withdraw early from treatment should attend a follow-up visit 14 days ± 3 days after the last dose of study treatment.

⁷ Serious adverse events are assessed from the time of consent as stated in study protocol Section 7.4.1.1

Pharmacokinetic/Pharmacodynamic Time and Events Table

PK/PD Sample	Day 1 (dose study med at clinic)	Day 15 (dose study med at home¹)	Day 29 (dose study med at clinic)
Plasma PK²	Pre-dose	1 st sample collected approx 6-10 hr post-dose on arrival. Additional sampling: 1, 2, and 3 h after this 1 st sample	Pre-dose, 1, 2, and 3 h post dose
EPO & VEGF²	Pre-dose	1 st sample collected approx 6-10 h post-dose on arrival. Additional sampling: 1, 2, and 3 h after this 1 st sample	Pre-dose and 3 h post dose
Hepcidin³	Pre-dose	Single sample during visit	Single sample during visit

¹ Subject to take their dose of study medication at home and arrive for clinic visit approx 6-10 h post-dose. Subjects may take their Day15 dose the evening prior to the Week 2 study visit to accommodate the 6-10 h PK/PD sampling window

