11.4.2.1. Treatment States for Laboratory Data, Vital Signs, ECG Data

For laboratory data, pre-dialysis vital signs, and ECGs, treatment state will be defined as:

Treatment State	Definition
Pre-Treatment	Date ≤ Study Treatment Start Date
On-Treatment	Study Treatment Start Date < Date ≤ Study Treatment Stop Date + 1
Post-Treatment	Date > Study Treatment Stop Date + 1

NOTES:

- If the study treatment stop date is missing then any assessment after study treatment Start Date will be considered to be On-Treatment.
- Post-dialysis vital signs measured on the "Study Treatment Start Date" will be considered to be On-Treatment.

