11.5.2. Baseline Definition & Derivations

11.5.2.1. Baseline Definitions

For Hgb the average of Hgb measured by the central lab, Quest, at Week -2 and Day 1 visits will serve as the baseline value. If an unscheduled Hgb value is taken pre-treatment then this will be slotted following the algorithm in Section 11.3.1 and Section 11.3.2.

Vital signs will be measured both pre-dialysis and post-dialysis. The baseline values for vital signs will be defined as:

Pre-dialysis baseline = vital sign value obtained pre-dialysis on Day 1

Post-dialysis baseline = vital sign value obtained post-dialysis at Week -2

Weight baseline= post-dialysis weight measured at Week -2.

Unless stated otherwise, the baseline value for all other lab parameters and ECG are defined as the last pre-treatment value observed. This is generally expected to be from the Day 1 visit (except for Folate, B12 and ECG, which are only measured at Week -4), although such values may be missing or unscheduled assessments may be performed before treatment start.

Parameter	Study Assessments Considered As Baseline			Baseline Used in Data Display
	Week -4	Week -2	Day 1 (Pre-Dose)	
Safety				
Vital Signs		X	X	See description above [1]
ECG	X			Week -4
Laboratory (clinical chemistry and hematology)		X	X	Day 1
Folate, Vitamin B12	X			Week -4
Ferritin, Transferrin, Total Iron, UIBC	X		X	Day 1
Efficacy				
Hgb		X	X	Mean (Quest) See description above
PK/PD				
PK Plasma, EPO & VEGF, Hepcidin			X	Day 1

NOTES:

- Three measurements of SBP, DBP and HR will be recorded at each study-specified visit and the mean of the replicate assessments will be used as the baseline value.

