11.5.2.2. Derivations and Handling of Missing Baseline Data

Definition	Reporting Details
Change from Baseline	= Post-Dose Visit Value – Baseline
% Change from Baseline	= 100 x [(Post-Baseline Visit Value – Baseline) / Baseline]
Maximum Change from Baseline	= Calculate the change from baseline at each given post-baseline timepoint and determine the maximum change

NOTES :

- Unless otherwise specified, the baseline definitions specified in Section 11.5.2.1 Baseline Definitions will be used for derivations for endpoints / parameters and indicated on summaries and listings.
- Unless otherwise stated, if baseline data is missing no derivation will be performed and will be set to missing.
- For this study %Change from Baseline (without log transformation) will be calculated only for “Absolute Reticulocyte Count.”

Some lab parameters will be log-transformed and percent change from baseline will be reported for these parameters: Hepcidin, Transferring Saturation, and VEGF.

To calculate a geometric mean for baseline measurement or at a specified timepoint, the following steps are used:

- Log-transform the data points

2. Calculate the mean and standard error (SE) of the log-transformed data
3. Exponentiate the mean, (if required, the mean – SE, mean + SE) and the endpoints of the confidence interval back to the original scale in order to obtain the geometric mean, (the geometric mean – SE, the geometric mean + SE) and the confidence interval for the geometric mean.
4. Coefficient of variation will be calculated as

$$CV = \sqrt{\exp(\text{Var}_{\log_{scale}}) - 1} \times 100\%$$

To calculate a geometric mean for the ratio of a specific timepoint to baseline (expressed as a percent change from baseline), the following steps are used:

1. Log-transform the data at both the baseline and the specified timepoint
2. For each subject, calculate a change from baseline using the log-transformed data
3. Calculate the mean and standard error (SE) of the log-transformed data
4. Exponentiate the mean, (if required, the mean – SE, the mean + SE) and the endpoints of the confidence interval, back to the original scale and then subtract 1, then multiply everything by 100% in order to express the geometric mean, (the geometric mean – SE, the geometric mean + SE) and the confidence interval (CI) as the percent change from baseline.

So, geometric mean for percent change from baseline =

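### Prior-ESA dose derivation: the fallback for a missing Week -2 weight is the same measurement, and after a break in dosing the gap factors can credit a day too many

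*SAP*

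**What the plan says.** **Weight.** In SAP 11.6.2 (Standardized rhEPO) every conversion formula divides by weight. The section specifies: "Note, weight is the weight recorded at screening Week -2". It then gives the fallback: "If the screening weight is missing, the baseline weight will be used". SAP 11.5.2.1 states: "Weight baseline= post-dialysis weight measured at Week -2". Under SAP 11.5.2.2, unless otherwise stated, "if baseline data is missing no derivation will be performed and will be set to missing". The schedule in SAP 11.2.1 notes: "Weight measured post-dialysis only & height measured at screening only". Vital signs are scheduled at Week -2, Day 1 and later visits. SAP 11.4.2.1 classes post-dialysis vital signs taken on the first dosing day as on-treatment.

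**Gap factors.** The same section averages the dose over the 12 weeks before randomization. Step 2 obtains a daily dose "by dividing the weekly dose from step 1 by 7". Step 3 lists gap factors of 2, 4, 7, 14, 21 and 28 days for regimens from three times weekly to four-weekly. Step 4 sets duration to stop date + gap factor - start date + 1, capped at the start of the next dose or at randomization. A record with frequency ONCE bypasses the gap factor and counts as exactly one dose.

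**The concern.** A fallback should supply a value when the first source is missing. Here both names point to one measurement, so the rule looks complete but does nothing. The affected subject loses the standardized prior rhEPO dose, which is a baseline characteristic (SAP 6.2.4), a histogram and a tertile subgroup (SAP 11.10.1). A usable weight was probably taken two weeks later.

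For the gap factors, the issue is whether the days credited to a dose match the interval it covers. If they do not, the same injection has a different value depending on whether it is coded with a regimen frequency or as ONCE.

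**Working it through.** **1. Weight rule**

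- First source: Week -2 weight (11.6.2).
- Fallback: baseline weight (11.6.2), which is the Week -2 post-dialysis weight (11.5.2.1).
- Weight is taken post-dialysis only, so the two are the same value.
- An unscheduled weight between Day -21 and Day -1 is slotted to Week -2 (11.3.1). It then fills both terms at once: the subject is kept, but the fallback has contributed nothing.
- With no such value, 11.5.2.2 leaves the result missing.
- The Day 1 post-dialysis weight is scheduled, but nothing in the plan lets it stand in.

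Size: 1% of 90 = 0.9 subject. At an assumed 2% missing, 0.02 × 90 = 1.8, about two subjects.

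**2. Gap factors**

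The plan's figures reproduce as pause threshold minus 1: 3-1, 5-1, 8-1, 15-1, 22-1 and 29-1 give 2, 4, 7, 14, 21 and 28.

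Days credited to one dose (start = stop), using gap + 1:

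| Regimen | Gap | Days credited | Interval | Excess |
|---|---|---|---|---|
| Weekly | 7 | 8 | 7 | 1/7 = 14.3% of that dose |
| 2-weekly | 14 | 15 | 14 | 1/14 = 7.1% |
| 3-weekly | 21 | 22 | 21 | 1/21 = 4.8% |
| 4-weekly | 28 | 29 | 28 | 1/28 = 3.6% |

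One full week of the more frequent regimens, using (stop - start) + gap + 1:

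- Three times weekly, Mon-Wed-Fri: 4 + 2 + 1 = 7 days, exact.
- Twice weekly: Mon/Wed 2 + 4 + 1 = 7; Mon/Thu 3 + 4 + 1 = 8; Mon/Fri 4 + 4 + 1 = 9.

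Effect on the 12-week average for the weekly or longer regimens: one extra day adds (weekly dose / 7) / 12 = weekly dose / 84, or 1.2% of the full weekly dose.

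Worked case: weekly dosing starts 84 days before randomization, with the last dose 14 days before it (11 doses).

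- As written: 70 + 7 + 1 = 78 days; 78/84 = 0.929 of the weekly dose.
- Gap of 6: 70 + 6 + 1 = 77 days; 77/84 = 0.917 = 11/12, the exact value.

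Same record with the last dose 7 days before randomization: 77 + 7 + 1 = 85 days, capped at 84. The excess disappears.

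**3. Pause and no-pause formulas**

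Step 4 prints the same capped expression for both cases. A gap of 6 used in both therefore credits min(8, 7) = 7 days when the next weekly dose comes after 8 days, and min(9, 7) = 7 when it comes after 9. Changing the gap for paused records only, and crediting unpaused ones to the next start, would give 8 and 7: a longer wait would earn less.

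**The case against.** **The design makes the extra day uncommon.** Protocol 5.2 (criterion 5) requires the same ESA, with limited dose variation, from 4 weeks before Day -28 through Day 1, which is 8 of the 12 weeks. Protocol 4.2 places Day 1 on the next ESA due date or as close as practicable. The last record is then usually capped. This stands and is why the second part is minor. It does not remove the fault: 4 of the 12 weeks lie outside the stability rule, and the timing of Day 1 is flexible.

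**The gap factors follow a consistent convention.** They do, as threshold minus 1. A one-day tolerance is sensible for detecting a pause. Credited as dose, however, it conflicts with the section's own ONCE rule, under which the same injection counts once.

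**The Day 1 weight is on-treatment.** That is correct under SAP 11.4.2.1. Using it only as a divisor in this derivation needs one sentence. Using it as baseline weight or BMI needs an explicit exception.

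**Stronger readings that a reader might infer.** One is that long-acting ESAs are generally over-credited relative to three-times-weekly epoetin. The documents do not support this. The cap removes the excess in uninterrupted dosing, twice-weekly schedules can gain as much or more, and the three-times-weekly row is exact only when the record ends at the close of a dosing week. For example, Monday to the following Monday gives 7 + 2 + 1 = 10 days for four doses worth 4 × 7/3 = 9.33. Another is that every subject without a scheduled Week -2 weight is lost. Slotting an unscheduled weight can prevent that.

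**Conclusion.** Both parts hold, and both are small. The weight fallback is circular as written. Its cost is any subject with no weight in the Week -2 window, a number the documents do not let one estimate. The gap factors over-credit by one day in weekly and longer regimens, and by up to two days in the twice-weekly schedules checked. This happens when a pause is flagged or the last dose falls more than one interval before randomization. For weekly and longer regimens it is about 1.2% of the full weekly dose in the 12-week average per occurrence.

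It would be wrong to infer an effect on the main results. The Emax model uses dose alone, the dose ratio is built from the dose-response fits, and the randomization strata use product-specific cut-offs rather than this derived variable. What is affected is the baseline display, the histogram and the tertile subgroup. The subgroup itself is not endangered by a few losses: with 90 ITT subjects, the 30% rule needs 27 per group and a full tertile holds 30.

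**What to change.** 1. In SAP 11.6.2, for this derivation, replace the baseline weight as fallback by the Day 1 post-dialysis weight or, if that is also missing, any other recorded screening weight. (Protocol 7.4.3 includes weight in the physical examination, which is scheduled at Week -4.) If the same fallback is wanted for baseline weight and BMI, amend 11.5.2.1 and add an exception to 11.4.2.1.
2. Set the gap factors for weekly, 2-, 3- and 4-weekly regimens to 6, 13, 20 and 27 days, so that the last dose earns exactly one interval. Keep the single capped formula for paused and unpaused records alike, or align the pause thresholds, so that a longer wait never earns less credit.
3. For twice-weekly dosing, state that the credit depends on the dosing days and is approximate; no single gap is exact for Mon/Wed, Mon/Thu and Mon/Fri together.

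The cost is a few sentences in the SAP and a few lines of derivation code, with no new data collection. The change should be made before unblinding.
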